## Postoperative variables of interest

1. Any nausea or vomiting postoperatively to 24 hours following surgical incision.
2. Any antiemetic usage postoperatively to 24 hours following surgical incision.
3. Nausea –
  - a. Worst nausea as measured on a numerical rating scale (numerical rating scale [NRS], 0–10) in PACU and post PACU up to the first 24 hours following surgical incision.

- b. Antiemetic usage in each of these periods.
4. Vomiting- Any vomiting and number of vomiting events in PACU and post PACU up to the first 24 hours following surgical incision.
  5. Highest pain score (NRS, 0–10) at rest and on movement in PACU and post PACU up to the first 24 hours following surgical incision.
  6. Quality of recovery score Day
  7. Sleep location night 1 and night 2
  8. Noise level night 1 and night 2
  9. Non-study dexamethasone intraoperative, PACU and day 1

These outcomes will be tabulated according to the treatment group but no formal comparison will be performed because we know that dexamethasone administration alters these outcome variables. It is also possible that these outcomes might interact with the sleep outcomes, but we do not plan to examine this. For non-normal continuous distributions, median regression via quantile regression will be undertaken. For binary outcomes, binomial regression to estimate risk ratios together with 95% CI will be undertaken. Should the regression model fail to converge, a linear model with identity link or Poisson model with logarithmic link (respectively) and robust standard errors will be employed.

\*\*\*\*\*TABLES\*\*\*\*\*  
\*\*\*\*\*

Table 1: Baseline characteristics of sleep subgroup population by treatment group

	Dexamethasone	Control
Age		
Sex		
Weight		
BMI		
ASA		
1/2		
3		
4		
Diabetes		
Chronic pain		
Opioid therapy for chronic pain		
Surgery type		
Length of surgery		
Planned use of opioids post-operatively		
PCA		
Neuraxial (intrathecal / epidural)		
Regular opioids (oral / intravenous / patch)		
PSQI score		

Sleep at home		
Sleep apnoea diagnosis		
CPAP regular use		

Table 2: Primary outcome analysis by mITT, per protocol and post-hoc adjustment for night one and secondary outcome night two.

Night	Method	Placebo	Dexamethasone	Difference (95% CI)	p-value	Missing
One (n)	mITT					
	Per protocol					
	Post-hoc adjustment					
Two (n)	mITT					

Results will be presented as a graph for night one and in table format. A graph of the estimates from the three methods will be presented (similar to a forest plot), with the non-inferiority margin ( $\Delta$ ) of -7.5 drawn in as a line.

[figure not shown]

Image as per Schumi, J., Wittes, J.T. Through the looking glass: understanding non-inferiority. *Trials* **12**, 106 (2011). <https://doi.org/10.1186/1745-6215-12-106>

Table 3: Variables of interest post randomisation.

	Dexamethasone	Control	Estimate (95% CI)	p-value
Any nausea or vomiting up to 24 hours post-surgery				
Any antiemetic up to 24 hours post-surgery				
Worst nausea rating PACU				
Anti-emetic PACU				
Anti-emetic Day 1				
Worst nausea rating Day 1				
Any vomiting PACU				
Any vomiting Day 1				
Number of vomiting events PACU				
Number of vomiting events Day 1				
Worst pain (movement) PACU				
Worst pain (rest) PACU				
Worst pain (movement) Day 1				
Worst pain (rest) Day 1				
Sleep location night 1				
Noise level (VAS score) night 1				
Sleep location night 2				
Noise level (VAS score) night 2				
Non-study DXA during surgery				
Non-study dexamethasone PACU				
Non-study dexamethasone Day 1				

Table 4: Individual components of the Quality of Sleep Questionnaire (will not test)

	Placebo	Dexamethasone
Night one		
My sleep last night was: light (0) - deep (100)		
Last night, the first time I got to sleep I: just never could not fall		

asleep (0) - fell asleep almost immediately (100)		
Last night I was: awake all night long (0) - awake very little (100)		
Last night, when I woke up or was awakened I: couldn't get back to sleep (0) - got back to sleep immediately (100)		
I would describe my sleep last night as: a bad night's sleep (0) - a good night's sleep (100)		
I would describe the noise level last night as: very noisy (0) - very quiet (100)		
Night two		
My sleep last night was: light (0) -deep (100)		
Last night, the first time I got to sleep I: just never could not fall asleep (0) - fell asleep almost immediately (100)		
Last night I was: awake all night long (0) - awake very little (100)		
Last night, when I woke up or was awakened I: couldn't get back to sleep (0) - got back to sleep immediately (100)		
I would describe my sleep last night as: a bad night's sleep (0) - a good night's sleep (100)		
I would describe the noise level last night as: very noisy (0) - very quiet (100)		

Name \_\_\_\_\_

Date \_\_\_\_\_

## Sleep Quality Assessment (PSQI)

### What is PSQI, and what is it measuring?

The Pittsburgh Sleep Quality Index (PSQI) is an effective instrument used to measure the quality and patterns of sleep in adults. It differentiates "poor" from "good" sleep quality by measuring seven areas (components): subjective sleep quality, sleep latency, sleep duration, habitual sleep efficiency, sleep disturbances, use of sleeping medications, and daytime dysfunction over the last month.

### INSTRUCTIONS:

The following questions relate to your usual sleep habits during the past month only. Your answers should indicate the most accurate reply for the majority of days and nights in the past month. Please answer all questions.

#### During the past month,

1. When have you usually gone to bed? \_\_\_\_\_
2. How long (in minutes) has it taken you to fall asleep each night? \_\_\_\_\_
3. What time have you usually gotten up in the morning? \_\_\_\_\_
4. A. How many hours of actual sleep did you get at night? \_\_\_\_\_  
 B. How many hours were you in bed? \_\_\_\_\_

5. During the past month, how often have you had trouble sleeping because you	Not during the past month (0)	Less than once a week (1)	Once or twice a week (2)	Three or more times a week (3)
A. Cannot get to sleep within 30 minutes				
B. Wake up in the middle of the night or early morning				
C. Have to get up to use the bathroom				
D. Cannot breathe comfortably				
E. Cough or snore loudly				
F. Feel too cold				
G. Feel too hot				
H. Have bad dreams				
I. Have pain				
J. Other reason (s), please describe, including how often you have had trouble sleeping because of this reason (s):				
6. During the past month, how often have you taken medicine (prescribed or "over the counter") to help you sleep?				
7. During the past month, how often have you had trouble staying awake while driving, eating meals, or engaging in social activity?				
8. During the past month, how much of a problem has it been for you to keep up enthusiasm to get things done?				
9. During the past month, how would you rate your sleep quality overall?	Very good (0)	Fairly good (1)	Fairly bad (2)	Very bad (3)

### Scoring

- |                    |  |          |
|--------------------|--|----------|
| Component 1 | #9 Score   | C1 _____ |
| Component 2 | #2 Score (<15min (0), 16-30min (1), 31-60 min (2), >60min (3))
+ #5a Score (if sum is equal 0=0; 1-2=1; 3-4=2; 5-6=3) | C2 _____ |
| Component 3 | #4 Score (>7(0), 6-7 (1), 5-6 (2), <5 (3))   | C3 _____ |
| Component 4 | (total # of hours asleep) / (total # of hours in bed) x 100
>85%=0, 75%-84%=1, 65%-74%=2, <65%=3                      | C4 _____ |
| Component 5 | # sum of scores 5b to 5j (0=0; 1-9=1; 10-18=2; 19-27=3)  | C5 _____ |
| Component 6 | #6 Score   | C6 _____ |
| Component 7 | #7 Score + #8 score (0=0; 1-2=1; 3-4=2; 5-6=3)   | C7 _____ |

Add the seven component scores together \_\_\_\_\_ Global PSQI \_\_\_\_\_

**A total score of "5" or greater is indicative of poor sleep quality.  
 If you scored "5" or more it is suggested that you discuss your sleep habits with a healthcare provider**

[figure not shown]
### Quality of Sleep Questionnaire

We would like to review the quality of your sleep last night.

Please answer the questions in relation to your SLEEP LAST NIGHT by putting a vertical mark on the line that best describes your response.

[figure not shown]
Example:

**1. Cats are better than dogs:**

[figure not shown]

\*\*\*\*\*  
\*\*\*\*\*

[figure not shown]
**1. My sleep last night was;**

[figure not shown]
**2. Last night, the first time I got to sleep I:**

[figure not shown]
**3. Last night I was:**

**4. Last night, when I woke up or was awakened, I;**

**5. I would describe my sleep last night as:**

6. I would describe the noise level last night as:

very noisy \_\_\_\_\_ very quiet  
0 100

7. I would describe my sleep at home as:

extremely poor; \_\_\_\_\_ excellent sleep;  
the worst I could imagine 0 100 solid and  
completely restful

Modified Richards-Campbell Sleep Questionnaire (RCSQ) for PADDI Substudy Version 1.2

#### Appendix 4

#### Quality of Sleep Questionnaire Substudy eCRF Page

##### Day 1.

Patient has diagnosed OSA?

Yes  No

Uses CPAP machine regularly?

Yes  No

Where did the patient sleep last night?

Ward  High dependency/ICU

1. My sleep last night was;

mm

2. Last night, the first time I got to sleep I:

mm

3. Last night I was:

mm

4. Last night, when I woke up or was awakened, I;

mm

5. I would describe my sleep last night as:

mm

6. I would describe the noise level last night as:

mm

7. I would describe my sleep at home as:

mm

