## General principles

The analysis and reporting of the results will follow the CONSORT guidelines. [1] Baseline characteristics will be tabulated by Dexamethasone and placebo groups using appropriate summary statistics and will include PSQI score. [2] Data for the primary endpoint will be derived from those patients enrolled into the PADDI-SLEEP substudy (those who completed the extra sleep questionnaires). Data for all endpoints will be analysed using the modified intention-to-treat (mITT) and per protocol (PP) populations, with the mITT analysis regarded as the principal analysis. Full definitions of mITT and PP are provided below.

Further sensitivity analyses will make post-hoc adjustment for any variables exhibiting substantial imbalance across treatment arms at baseline (Table 1). Interpretation of all endpoints will be based on post estimates, confidence intervals and P-values. A nominal 5% significance level will be employed.

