### B. Per Protocol (PP) population

[figure not shown]
The PP population will comprise those patients who completed the treatment to which they were originally allocated, meaning ONLY those patients who receive a single dose of study drug or placebo according to their original randomised allocation. This analysis specifically excludes patients who were not given their randomised study drug at the commencement of surgery **AND** patients who received their study drug but also receive non-study glucocorticoid within the 24 hours following surgery. This also excludes patients randomised to dexamethasone whose randomisation was overridden and received open-label dexamethasone within the 24 hours following surgery. Patients who withdraw consent will have their data used up until the time of withdrawal.

The primary analyses will be in the mITT population, per protocol (PP) populations and a sensitivity analyses will make post-hoc adjustment for any variables exhibiting substantial imbalance across treatment arms at baseline. The mITT analysis will be undertaken as per the main Statistical Analysis Plan for the PADDI trial. The per protocol analysis will only exclude those who did not get the study drug or those who got non-study dexamethasone during surgery or in PACU, that is they received non-study dexamethasone prior to the primary outcome occurrence. Because the patients not meeting the PP population definition have been excluded, there may no longer be balance in patient characteristics between dexamethasone and placebo arms. The baseline and pre-operative characteristics in the dexamethasone and

placebo arms will be tabulated and compared for the 'compliant' (PP) patients. Any variables exhibiting imbalance will be adjusted for.

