## Outcomes

The primary outcome is sleep quality on night one (as assessed using the RCSQ). As the distribution of the sleep score is not normal, median regression will be undertaken to assess the difference in medians between the two treatment groups. For the sensitivity analysis, baseline characteristics will be examined and adjustment will be made for differences between the groups. The variable, preop sleep quality, is considered a major confounder and will be included in the adjusted models.

Histogram of sleep quality night one showing two peaks.

The secondary outcome is sleep quality on night two. The same analysis will be undertaken as per night one. Some people would have been discharged on day 1 but for consistency the same variables will be adjusted for as for night one in the sensitivity analysis.

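### Sleep at home is treated as a baseline covariate, but the only forms shown record it on postoperative Day 1, beside the primary outcome

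*SAP*

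**What the plan says.** Under General principles the SAP sets the adjustment rule: "Further sensitivity analyses will make post-hoc adjustment for any variables exhibiting substantial imbalance across treatment arms at baseline (Table 1"). The Per Protocol section applies a similar rule to that population, after comparing its baseline and preoperative characteristics: "Any variables exhibiting imbalance will be adjusted for".

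The pool is "Table 1: Baseline characteristics of sleep subgroup population by treatment group". Its rows include PSQI score, Sleep at home and "Length of surgery".

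The sleep questionnaire asks the patient to rate last night on 0-100 lines. Items 1 to 5 rate sleep, item 6 rates noise, and item 7 rates sleep at home. The substudy eCRF page headed Day 1 records the same items in the same order, ending with "7. I would describe my sleep at home as".

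On the timing of study drug, the Per Protocol section excludes "patients who were not given their randomised study drug at the commencement of surgery", so dosing is planned for the start of the operation.

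The Outcomes section adds one covariate regardless of imbalance: "The variable, preop sleep quality, is considered a major confounder and will be included in the adjusted models". No row of Table 1 carries that name.

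**The concern.** A baseline covariate is safe to adjust for because treatment cannot have changed it. On the forms shown, Sleep at home lacks that protection. It is a subjective rating, given after randomisation, after dosing and after the outcome night, on the same kind of line and the same sheet as the outcome. If a bad night shifts how a patient rates usual sleep, and treatment affects the night, then treatment affects the covariate. Adjusting for it then removes part of the treatment effect or adds to it.

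The selection rule compounds this. A difference between arms on item 7 that treatment itself produced would count as imbalance and help bring the variable into the model.

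At stake are the post-hoc adjusted row of Table 2 and possibly the per-protocol estimate. Both are to be plotted beside the mITT estimate against the non-inferiority margin, where readers will use them to judge robustness.

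**Working it through.** **Timing, from the SAP alone**

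| Variable | Status in SAP | When recorded, on the forms shown | Open to an effect of treatment? |
|---|---|---|---|
| PSQI score | Table 1; named as baseline in General principles | Asks about the past month; form undated | Not if completed before surgery |
| Sleep at home | Table 1 | Item 7, postoperative questionnaire and Day 1 eCRF | Yes, if last night colours the rating |
| Length of surgery | Table 1 | Known only once surgery ends, after dosing | Formally yes; no mechanism given |
| OSA diagnosis, CPAP use | Table 1 | Also on the Day 1 eCRF | Unlikely; facts of history |

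**Size: an illustration**

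The SAP gives no figure on this point to reproduce. From its Sample size section I take the margin of 7.5 mm and the RCSQ standard deviation of 25.28 mm. Everything else is assumed:
- true effect τ = -7.5 mm (dexamethasone minus placebo);
- true home sleep H0, with the same SD as the outcome Y and within-arm correlation ρ of 0.3 to 0.5 with it;
- recorded rating H = H0 + c·Y, up to a constant, where c is the carry-over in mm per mm of last night's score.

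Treatment then shifts H by c·τ. The within-arm slope of Y on H is

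β = (ρ + c) / (1 + 2cρ + c²)

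and the adjusted effect is τ - β·c·τ.

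| ρ | c | β | Shift in H (mm) | Adjusted effect (mm) |
|---|---|---|---|---|
| 0.3 | 0.1 | 1.07-denominator: 0.4/1.07 = 0.374 | -0.75 | -7.5 + 0.28 = -7.22 |
| 0.3 | 0.3 | 0.6/1.27 = 0.472 | -2.25 | -7.5 + 1.06 = -6.44 |
| 0.5 | 0.1 | 0.6/1.11 = 0.541 | -0.75 | -7.5 + 0.41 = -7.09 |
| 0.5 | 0.3 | 0.8/1.39 = 0.576 | -2.25 | -7.5 + 1.29 = -6.21 |
| 0.3 | -0.2 | 0.1/0.92 = 0.109 | +1.5 | -7.5 - 0.16 = -7.66 |
| 0.5 | -0.2 | 0.3/0.84 = 0.357 | +1.5 | -7.5 - 0.54 = -8.04 |
| either | 0 | ρ | 0 | -7.5 |

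Simulated linear models agree within simulation error. Under these normal assumptions the conditional median equals the conditional mean, so the result carries over to median regression. The SAP reports a two-peaked score, so real data would depart from these values.

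Positive carry-over shrinks the effect by 0.28 to 1.29 mm, or 4% to 17% of the margin (0.28/7.5 and 1.29/7.5). A contrast effect, where a bad hospital night makes home sleep look better, moves the estimate away from zero as long as c lies between -ρ and 0. A contrast stronger than ρ would shrink it again.

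**The case against.** The strongest reply is that the principal result is untouched. The SAP makes mITT the principal analysis and describes covariate adjustment as a sensitivity analysis with its own row in Table 2, so a distortion could show as a gap between rows. That stands, and it limits the weight of the point. It does not remove it: the Per Protocol section names the adjusted analysis alongside mITT and per-protocol as the primary analyses, and a robustness check that may itself be biased gives less reassurance.

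Second, the shift may be too small to trigger adjustment. Taking 25.28 mm as the SD of item 7 (an assumption), a shift of 0.75 to 2.25 mm is a standardised difference of 0.03 to 0.09, hardly substantial imbalance. The bias is also small beside a 95% confidence half-width of about 5.0 mm (1.96 × 25.28 × √(2/195), means approximation). This is fair. Chance imbalance would usually be needed as well. However, the SAP sets no threshold, and the per-protocol rule does not require the imbalance to be substantial.

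Three stronger readings are tempting, and the SAP does not support them:
- **That the plan is tilted towards non-inferiority.** The direction depends on a carry-over that nobody has measured, and zero is possible.
- **That adjusting for Length of surgery biases the effect.** Nothing in the SAP suggests that the drug changes operating time, and the per-protocol wording on baseline and preoperative characteristics arguably excludes it.
- **That item 7 is the mandatory sleep covariate.** PSQI is the natural reading, since General principles names it as baseline. The term is merely undefined.

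Finally, the protocol and baseline forms are not at hand, so a preoperative collection of Sleep at home cannot be ruled out. The SAP shows none.

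**Conclusion.** The point holds as a limited one. On the forms the SAP shows, a subjective rating made after treatment and beside the outcome is labelled baseline and is eligible for the adjusted and per-protocol models. The possible bias is of unknown size and either direction: roughly 0.3 to 1.3 mm towards zero for assumed carry-over of 0.1 to 0.3, roughly 0.2 to 0.5 mm away from zero for a contrast of -0.2, and none without carry-over. These values rest on assumed correlations and carry-over, not on trial data. The unadjusted mITT estimate is unaffected. Length of surgery is misclassified as to timing, with no demonstrated consequence. The change is worth making because it costs little and settles which sleep variable must be in the adjusted models.

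**What to change.** Amend the SAP as follows:
1. In General principles and the Per Protocol section, state that only variables measured before study drug may be adjusted for.
2. In Outcomes, define the preoperative sleep covariate as the PSQI global score, after confirming that it was completed before surgery.
3. Keep Sleep at home and Length of surgery as descriptive rows, footnoted as recorded on postoperative Day 1 and as intraoperative, and remove both from the adjustment pool. If a preoperative record of Sleep at home exists, cite that form and use that value instead.

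The cost is a few sentences and a table footnote, with no new data. The one loss is a possible prognostic covariate in the sensitivity models; PSQI, already collected, should recover some of that information.
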